### 9.3.1.3 Classification of exposure

Particular care will be taken in the definition and classification of paternal exposure. Person-time exposed will be classified to take into account intensity of drug exposure during the 3-months pre-conception risk window using the longitudinal K-means clustering (R package kml) algorithm (15). This method allows for a more precise description of exposure of fathers to drugs and allows profiles to be distinguished improving evaluation of effects of drugs on outcomes. In summary the following steps apply:

- To quantify drug exposure, for each individual, prescription data will be transformed into the standard units of measurement of the World Health Organization (WHO): the Defined Daily Dose (DDD) (Figure 8). The duration of treatment and dates of exposure

 See footnote 10

will be estimated assuming individuals are exposed to one DDD per day and using information on number of units and dates of prescriptions, where available. For the father, drug prescribed and dispensed three months before the LMP2 date (including the LMP2 date) will be taken into account. A validation of the assumption that individuals are exposed to one DDD per day will be provided as a sensitivity analysis (section 9.7.5).

- After super imposing length of exposure onto the spermatogenic risk window, exposure data will be individually transformed into number of DDDs (Figure 8) dispensed during every 14 day interval within the 3-months exposure period. This way, the cumulative drug exposure of each father will be evaluated at several time points, and the exposure data will become longitudinal which will allow drawing individual trajectories of exposure through the pre-conception period. Data will be censored at the LMP2 date.

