8. *Validation of the assumption that individuals are exposed to one DDD per day.* WHO DDD is the assumed average maintenance dose per day for a drug used for its main indication (i.e. epilepsy for valproate, lamotrigine and levetiracetam) in adults. This does not necessarily reflect the recommended or Prescribed Daily Dose. Therapeutic doses for individual patients and patient groups will often differ from the DDD as they will be based on individual characteristics (such as indication, age, weight, ethnic differences, type and severity of disease) and pharmacokinetic considerations. A comparison (ratio) between the distribution of estimated treatment durations (expected) and time between prescriptions (observed) will be provided with the caveat that this will necessarily be affected by the DDD methodology approximation. In order to partially overcome this limitation, this comparison will be provided separately for patients with and without an indication of epilepsy, as epilepsy is the main indication for the medicines at study therefore the indication used by WHO to estimate DDD. It is expected that the use of WHO DDD will be a better approximation of the observed treatment duration among patients with a diagnosis of epilepsy, with a ratio closer to one than for other indications. The distribution of estimated treatment durations (expected) will be compared to the distribution of time between prescriptions (observed), *separately for lamotrigine, levetiracetam, valproate and for patients with and without an indication for epilepsy*, using the following formulas:

Observed time between prescriptions for patient i is

$$\sum_{j=1}^{k-1} \text{days} (\text{prescription}_{j+1} - \text{prescription}_j)$$

where k is the number of prescriptions for each patient.

Expected treatment duration for patient i is

$$\frac{\sum_{j=1}^{k-1} n. \text{pkg in prescription}_j * n. \text{dosage unit in each pkg}}{\text{WHO DDD}}$$

where k is the number of prescriptions for each patient.

The ratio of Observed over Expected for patient i is

$$\begin{aligned} \sum_{j=1}^{k-1} \text{days} (\text{prescription}_{j+1} - \text{prescription}_j) / \frac{\sum_{j=1}^{k-1} n. \text{pkg in prescription}_j * n. \text{dosage unit in each pkg}}{\text{WHO DDD}} &= \\ &= \sum_{j=1}^{k-1} \frac{\text{days} (\text{prescription}_{j+1} - \text{prescription}_j) * \text{WHO DDD}}{n. \text{pkg in prescription}_j * n. \text{dosage unit in each pkg}} \end{aligned}$$

The ratio for the population

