$$\sum_{i=1}^n \left( \frac{\sum_{j=1}^{k-1} \text{days} (\text{prescription}_{j+1} - \text{prescription}_j) * \text{WHO DDD}}{n. \text{pkg in prescription}_j * n. \text{dosage unit in each pkg}} \right) / n$$

where n is the number of patients and k is the number of prescriptions per patient.

Under the assumption of perfect compliance of each patient, if the Ratio for the overall population is between 0.8 and 1.2 then the WHO DDD is a good approximation of the reality; the more the ratio departs from the good approximation range the more the real daily dose prescribed diverge from the WHO defined daily dose. It is expected to have a good approximation to the reality for patients with the epilepsy indication for AEDs.

This measure will be affected both from the approximation of using the WHO DDD and the compliance of patients to the treatment. The less the compliance, the more the ratio departs from good approximation (0.8-1.2). Since the dose prescribed is not available, it will not be possible to assess what affected more the results.

Sensitivity analysis 8 will be performed only in the Primary Outcome Cohort for Descriptive Analyses

9. *Narrow case definition for secondary outcome - focus on CM in live births*: Since the population for analysis of the secondary outcome for Sweden is comprised of live births, the distribution of CM observed in this population is likely to reflect functional defects and minor morphological abnormalities, rather than major morphological abnormalities (usually associated with fatal outcome during gestation). A sensitivity analysis will therefore be performed on the corresponding live birth population for Norway and Denmark to describe the corresponding risk and underlying distribution of CM associated with live births.
10. *Continuous measure of cumulative exposure*: Investigate separately the risk of NDD, including ASD, as well as CM, in offspring paternally exposed to monotherapy treatment with valproate, lamotrigine or levetiracetam at the time of conception, using cumulative exposure to treatment. Cumulative exposure will be calculated as the total amount of DDD intake that a father is exposed to over the 3-months time window prior to LMP2 date, i.e. the sum of the DDD in all 14-day intervals as reported in Figure 8.

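### Sensitivity analysis 8 equates a ratio of sums with a sum of ratios, so its DDD check grows with the number of refills and the 0.8–1.2 range is applied to the wrong quantity

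*Protocol*

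**What the plan says.** Section 9.3.1.3 of the Protocol promises the check: "A validation of the assumption that individuals are exposed to one DDD per day will be provided as a sensitivity analysis". Section 9.7.5, item 8, defines it.

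- "Observed time between prescriptions for patient i is" followed by the sum, over j = 1 to k−1, of the days from prescription j to prescription j+1, "where k is the number of prescriptions for each patient".
- "Expected treatment duration for patient i is" followed by the sum, over the same j, of packs times dosage units, divided by the WHO DDD.
- "The ratio of Observed over Expected for patient i is" followed by two lines joined by an equals sign. The first divides the observed sum by the expected sum. The second is a single sum over j of days times DDD divided by that prescription's amount.
- The population ratio builds on the second line, sums over patients and divides by n, "where n is the number of patients and k is the number of prescriptions per patient".

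The decision rule, under perfect compliance, is "if the Ratio for the overall population is between 0.8 and 1.2 then the WHO DDD is a good approximation of the reality". Results are to be given by drug and by epilepsy indication, and fathers with epilepsy are expected to show a better fit, "with a ratio closer to one than for other indications". The intended value under a correct DDD is therefore 1.

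**The concern.** A quotient of two sums is not the sum of the quotients. The second line adds up one ratio per refill interval, so it rises with the number of intervals even when every refill agrees exactly with one DDD per day. The population formula inherits this, since n counts patients and nothing divides by k−1.

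One DDD per day determines the drug-use periods (footnote 10 in Section 9.3.1.1), the treatment dates and 14-day DDD counts that feed the k-means clusters (Section 9.3.1.3), and cumulative exposure in sensitivity analysis 10. The check named as validating that assumption should not depend on how often prescriptions are filled. As printed it does, and a difference in refill counts between drugs or indications would read as a difference in how well the DDD fits.

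**Working it through.** **Inputs.** The formulas, the perfect-compliance condition and the 0.8–1.2 range come from Section 9.7.5, item 8. The valproate DDD of 1.5 g comes from the caption material of Figure 8 in Section 9.3.1.3. The number of prescriptions k, the pack amounts and the refill days below are assumptions, because the protocol gives none for this check.

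**Notation.** For interval j, d_j is days to the next prescription, a_j the amount dispensed, D the DDD, s_j = a_j/D the days of supply, and r_j = d_j/s_j.

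- Form A (first line): Σd_j / (Σa_j/D) = Σd_j / Σs_j
- Form B (second line): Σ(d_j·D/a_j) = Σr_j

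**Step 1, in general.** Form A equals Σ(s_j·r_j)/Σs_j, an average of the r_j weighted by supply, so it cannot exceed the largest r_j. Form B adds all the r_j. With one interval (k = 2) the forms agree. With two or more intervals of positive length, B is always larger than A.

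**Step 2, exactly one DDD per day.** Take 135 g of valproate per dispensation, so s_j = 135/1.5 = 90 days, and a refill every 90 days. Each r_j = 90×1.5/135 = 1.

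| Prescriptions k | Form A | Form B |
|---|---|---|
| 2 | 90/90 = 1 | 1 |
| 3 | 180/180 = 1 | 2 |
| 4 | 270/270 = 1 | 3 |
| 5 | 360/360 = 1 | 4 |

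Form A gives the intended 1 throughout. Form B gives k−1.

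**Step 3, unequal refills.** Days 30, 90, 60 against supplies of 30, 100, 50 days. Form A = 180/180 = 1.00. Form B = 1.00 + 0.90 + 1.20 = 3.10.

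**Step 4, population mean under a correct DDD.** The mean of form B equals the mean number of intervals, so the check fails once that mean passes 1.2. If fathers have one or two intervals only and a share p has two, the mean is 1 + p, which exceeds 1.2 when p > 0.20. A simulation of 5,000 fathers with 1 to 6 intervals (mean 3.51) and refills within ±10% of one DDD per day gave a mean of 1.00 for form A and 3.52 for form B.

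**Step 5, a wrong DDD.** If true use is 2 DDD per day, each r_j = 0.5, so A = 0.50 for any k. With two intervals B = 0.5 + 0.5 = 1.00, inside the range. At 3 DDD per day with three intervals, A = 0.33 and B = 1.00.

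**Step 6, comparison between groups.** Two groups, both at exactly one DDD per day, averaging two and four intervals, score 2 and 4 on form B. Both score 1 on form A.

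**Step 7, layout of the population formula.** In the available text the population fraction has the sum over j in its numerator only, above a single prescription's amount. With equal packs that also gives Σd_j/s = k−1. With the refills of step 3 and the average supply of 60 days it gives 180/60 = 3.00. This layout does not return the intended 1 either.

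**The case against.** Several points on the other side stand.

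- The intent is right. Observed and Expected are each defined correctly and the first line is the correct quotient. An analyst who coded that line has the right patient ratio, and the document cannot show which line was coded.
- This is a descriptive check, confined to the descriptive cohort of the primary outcome. No passage redefines exposure or re-runs a model if the ratio leaves 0.8–1.2, and item 8 already concedes that DDD error and non-compliance cannot be separated.
- The size depends on k, which the protocol does not give. A reader might extrapolate to ratios of 8 or 12 for fathers with 9 or 13 prescriptions. Nothing in the documents supports those counts. If the Swedish extraction window of Section 9.2.2 applied here (192 days before to 28 days after LMP2, 220 days, an assumption), 9 prescriptions would need refills every 220/8 = 27.5 days.
- A reader might infer that the check can never pass. It is correct for two-prescription fathers, and a group made up mainly of them would score properly.
- A reader might add that Expected lacks a tablet-strength term. That holds only if the dosage unit is a count. The term is not defined, and Figure 8, which works the calculation, is not visible in the available text, so the point is not established.

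None of this repairs the equality. No other section corrects it, and a layout problem in text extraction does not explain it, since both printed forms give k−1 with equal packs.

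**Conclusion.** The formula is wrong as written. The second line of the patient ratio does not follow from the first when k > 2, and the population ratio averages the wrong form. Under perfect compliance at exactly one DDD per day the printed value is k−1, so a correct DDD is rejected once the mean number of intervals exceeds 1.2. For any father with more than one interval the printed ratio is too high, which also lets heavier true use pass as one DDD per day. The direction is certain; the size is unknown without k and the prescription window.

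A reader might conclude that the exposure classification or the primary result is thereby invalid. The documents do not support that. The formula tests the DDD assumption but does not set it, and the first Cox model in Section 9.7.3.2.1 compares a dichotomous exposure without using the clusters. What is at stake is whether sensitivity analysis 8 can be read as evidence for or against the DDD assumption. This is a should-fix.

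**What to change.** In Section 9.7.5, item 8:

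- Delete the second line of the patient formula. Define R_i = Σd_j·D / Σa_j for j = 1 to k−1.
- Define the population ratio as ΣR_i / n and apply 0.8–1.2 to that. This keeps the plan's own choice of a mean over patients. Dividing the sum of ratios by k−1 would remove most of the error but is not the same quantity (3.10/3 = 1.03 against 1.00 in step 3).
- State the prescription window and report the distribution of k by drug and indication.

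Section 6 lists a compilation of sensitivity tables dated 27 March 2023 and Norwegian re-run deliverables due 23 October 2023, so the analysis may already exist. The sponsor should confirm which form was programmed. If it was the first line, only the text changes. If it was the printed population formula, the tables need re-running: three countries by three drugs by two indication groups is up to 18 ratios, on data already held.

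### The DDD-validation ratio in sensitivity analysis 8 is rewritten as a sum of interval ratios, so it equals the number of refill intervals rather than 1 when fathers take exactly one DDD per day

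*Protocol*

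**What the plan says.** Sensitivity analysis 8 in Protocol section 9.7.5 builds its statistic in four steps.

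- **Observed.** "Observed time between prescriptions for patient i is" followed by the sum, over j = 1 to k-1, of the days between consecutive prescriptions.
- **Expected.** "Expected treatment duration for patient i is" followed by the sum, over the same k-1 prescriptions, of packages times dosage units, divided by the WHO DDD. In both, k is defined by "where k is the number of prescriptions for each patient".
- **Patient ratio.** "The ratio of Observed over Expected for patient i is" followed by two lines joined by an equals sign. The first is the observed total over the expected total. The second is the sum over j of days times DDD divided by packages times units, interval by interval.
- **Population ratio.** An expression modelled on the second line, summed over patients and divided by n, "where n is the number of patients and k is the number of prescriptions per patient". Nothing divides by k-1.

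The decision rule presumes that all fathers comply fully. It reads "if the Ratio for the overall population is between 0.8 and 1.2 then the WHO DDD is a good approximation of the reality" and so has 1 as its intended target: for patients with epilepsy the text expects better agreement, "with a ratio closer to one than for other indications". Results are to be shown separately by drug and by epilepsy indication.

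**The concern.** A ratio of two sums is not the sum of the ratios. The ratio of totals is a weighted average of the interval ratios, so it stays near 1 when each interval ratio is near 1. The sum of the interval ratios adds roughly 1 for every further prescription. The range 0.8 to 1.2 makes sense only for the first.

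Section 9.3.1.3 names this analysis as the validation of the one-DDD-per-day assumption. That assumption determines treatment duration and dates, the 14-day trajectories and the k-means clusters; it also feeds the cumulative-exposure analysis (sensitivity analysis 10). If the summed form is computed, a correct assumption can appear to fail and a wrong one can appear to hold. A difference in refill counts between drugs, or between fathers with and without epilepsy, would look like a difference in dosing. The protocol attributes departures from the range only to the DDD approximation and to compliance, so a reader would misread the artefact.

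**Working it through.** **Notation.** For one father let d_j be the days in refill interval j, and S_j the supply from prescription j expressed in DDDs (dispensed amount divided by the WHO DDD), j = 1 to k-1. This takes the expected duration to be in days, as the text intends.

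- Form A, first line: (Σ d_j) / (Σ S_j).
- Form B, second line: Σ (d_j / S_j).

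**Are they equal?** Form A is an average of the ratios d_j/S_j with weights S_j/ΣS_j. With positive values, an average of two or more ratios is smaller than their sum. The equality therefore holds only at k = 2.

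**Numerical example.** Intervals of 30, 120 and 90 days; supplies of 90, 90 and 60 DDDs (k = 4).

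- Form A: 240/240 = 1.00.
- Form B: 30/90 + 120/90 + 90/60 = 0.33 + 1.33 + 1.50 = 3.17.

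**Value under the protocol's own condition.** With perfect compliance at one DDD per day and refill at run-out, d_j = S_j and every interval ratio is 1. The DDD value and the pack sizes cancel.

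| k | Form A | Form B = k-1 |
|---|---|---|
| 2 | 1.00 | 1 |
| 3 | 1.00 | 2 |
| 4 | 1.00 | 3 |
| 5 | 1.00 | 4 |
| 7 | 1.00 | 6 |
| 13 | 1.00 | 12 |

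So the target of 1 is reproduced by form A at every k, and by form B only at k = 2.

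**Value at another true dose.** If a father takes c DDD per day, d_j = S_j/c and form B is (k-1)/c.

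- c = 2, k = 3: 2/2 = 1.0, a pass.
- c = 3, k = 4: 3/3 = 1.0, a pass.
- To fall within 0.8 to 1.2, c must lie between (k-1)/1.2 and (k-1)/0.8. At k = 3 that is 1.67 to 2.5 DDD per day; at k = 5 it is 3.33 to 5.0.

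**Population level.** Averaged over fathers at one DDD per day, form B gives the mean of k_i - 1. It exceeds 1.2 once mean k exceeds 2.2. In 1,000 simulated fathers with k drawn from 2 to 6 (an assumed distribution), form A averaged 1.00 and form B 3.05, which is the mean of k-1.

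**Imperfect refill timing.** With k = 5, supplies of 60 DDDs and refill dates moved by up to 10 days either way, three runs gave form A of 0.98, 1.00 and 1.08, and form B of 3.92, 4.02 and 4.30.

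**The population formula read literally.** As typeset, its inner sum stands over the numerator only, which leaves index j undefined in the denominator. With equal packs that again gives k-1. With unequal packs the value depends on which j is used; one example at k = 5 ran from 2.9 to 9.7. Neither case returns 1 for k above 2.

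**The case against.** The strongest reply is that the statistic is defined correctly before it is rearranged. The observed and expected definitions, and the first line of the patient ratio, give 1, and the prose makes the intent clear, so a careful programmer might use the right form. The population formula is also not typeset identically to the second line. A summation sign may be missing from its denominator, which would restore the ratio of totals.

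Several points of this stand. Intent is recoverable, and the program is not visible. The value k-1 is firm for the second line, while for the population formula it depends on the reading. The protocol fixes neither the period over which prescriptions are counted nor a refill interval, so no particular k can be asserted. If only the six months before conception counted (footnote 10 to section 9.3.1.1) with three-monthly refills, both being assumptions here, k would be about 2 to 3 and the value about 1 to 2. The analysis is descriptive, and no exposure definition or model is said to change with its result. The planned comparison of the observed and expected distributions does not use the faulty line.

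None of this rescues the formula. A lost summation sign in the population formula would still leave the patient-level equality false, and the protocol would then offer two unequal definitions as one.

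**Conclusion.** The formula is wrong as written. The stated equality fails for every father with more than two prescriptions. The population ratio modelled on it, judged against 0.8 to 1.2, does not return 1 when the assumption being tested is true. Under perfect compliance at one DDD per day the summed form gives k-1 per father and the mean of k-1 over the population, so a group with mean k above 2.2 fails a correct assumption.

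The exact value k-1 assumes refill at run-out and an expected duration expressed in days; modest timing error barely moves it. The specific values of k are illustrations. The effect is limited to sensitivity analysis 8 and does not alter the primary hazard ratio. It should still be corrected, because this is the check the protocol offers in support of its exposure measure.

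**What to change.** In section 9.7.5, sensitivity analysis 8:

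1. Delete the second line of the patient ratio. Define the ratio as days from first to last prescription divided by total expected days supplied by prescriptions 1 to k-1.
2. Put that same quantity in the population formula, with explicit sums in both numerator and denominator, and divide by n.
3. Restrict to fathers with at least two prescriptions. With k = 1 the correct ratio is 0/0, while the summed form contributes a spurious 0.

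Dividing the summed form by k-1 would also give 1 under perfect use, but it weights each interval equally whatever its supply; the ratio of totals matches the definitions already printed.

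Confirm which form was programmed. If the ratio of totals was used, the cost is a text correction. If the summed form was used, the program must be corrected, the analysis rerun in each country, and the affected tables reissued; Table 1 in section 6 dates the annex of sensitivity tables 27 March 2023. No new data are needed.

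### Sensitivity analysis 8 sets out to validate one DDD per day for individuals, but its pass rule looks only at the population mean ratio, in which high and low doses cancel

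*Protocol*

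**What the plan says.** Section 9.3.1.3 estimates treatment duration and exposure dates at one DDD per day and promises a check: "A validation of the assumption that individuals are exposed to one DDD per day will be provided as a sensitivity analysis". Item 8 of section 9.7.5 carries the matching title, "Validation of the assumption that individuals are exposed to one DDD per day", and so states its target at the level of the individual.

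The item defines an observed/expected ratio for each patient, sums these ratios over patients and divides by n ("where n is the number of patients and k is the number of prescriptions per patient"). The verdict is then conditional: "Under the assumption of perfect compliance of each patient", the rule is that "if the Ratio for the overall population is between 0.8 and 1.2 then the WHO DDD is a good approximation of the reality". No criterion is set on how far the per-patient ratios spread or on what share of them lies near 1.

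Two other parts of the item bear on this. The comparison of expected with observed durations is to be given "separately for lamotrigine, levetiracetam, valproate and for patients with and without an indication for epilepsy", and it is described as a comparison of distributions. The item also expects variation between patients: "Therapeutic doses for individual patients and patient groups will often differ from the DDD as they will be based on individual characteristics".

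**The concern.** The assumption is applied father by father. Footnote 10 (section 9.3.1.1) turns each prescription into treated days at one DDD per day. This decides which dispensations from the six months before conception reach the three-month window. Section 9.3.1.3 builds each father's 14-day trajectory and k-means cluster on the same basis, and sensitivity analysis 10 sums each father's DDDs.

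A correct average does not repair wrong individual dates. As an illustration with assumed figures, 100 DDDs dispensed 160 days before LMP2 last until day -60 at one DDD per day, which is inside the window. At two DDDs per day they last 50 days and run out on day -110, before the window opens.

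This is the protocol's only check of the assumption. If it passes on the mean alone, the report could present an individual-level assumption as validated when many fathers are far from it.

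**Working it through.** **Inputs.** The band 0.8 to 1.2, the mean over n patients and the perfect-compliance condition all come from item 8 of section 9.7.5. The band is a chosen threshold, so there is no figure in the plan to reproduce. The protocol gives no SD or CV for dose; the spreads below are assumptions, shown as a range.

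**Per-patient ratio.** Take each ratio as total observed days divided by total expected days, the ratio of sums with which item 8 starts. Under perfect compliance, a father taking d DDDs per day has R = 1/d. At exactly one DDD per day, with 90 DDDs collected every 90 days, R = 1.0 for any number of prescriptions k.

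**Log-normal dose, median m, log-SD s.**

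- Mean ratio = exp(−ln m + s²/2).
- Share in band = Φ((ln 1.2 + ln m)/s) − Φ((ln 0.8 + ln m)/s).

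| m | s | Mean ratio | Share in band | Rule |
|---|---|---|---|---|
| 1.0 | 0.3 | exp(0.045) = 1.05 | Φ(0.61) − Φ(−0.74) = 50% | pass |
| 1.0 | 0.5 | exp(0.125) = 1.13 | Φ(0.36) − Φ(−0.45) = 31% | pass |
| 1.2 | 0.6 | exp(−0.182 + 0.180) = 1.00 | Φ(0.61) − Φ(−0.07) = 26% | pass |
| 1.0 | 0.7 | exp(0.245) = 1.28 | not needed | fail |

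With the median at one DDD, the rule starts to fail when s²/2 exceeds ln 1.2 = 0.182, that is, for s above about 0.60.

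**Mean ratio held at exactly 1 (log-normal R).** The share in band is 95% at CV 0.1, 51% at CV 0.3, 33% at CV 0.5 and 18% at CV 1. All four populations pass.

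**Two-group mixtures, half of fathers in each group.**

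- Doses 0.6 and 2.0 DDD per day: (1/0.6 + 1/2.0)/2 = (1.667 + 0.5)/2 = 1.08. The rule passes with 0% in band.
- Doses 0.67 and 2.0 DDD per day: (1.5 + 0.5)/2 = 1.00. The rule passes with 0% in band.

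**Separate matter.** The printed algebra in item 8 equates a ratio of sums with a sum of ratios. As printed, a father on exactly one DDD per day scores k − 1 (2 at k = 3, 4 at k = 5). The figures above use the ratio of sums and do not depend on that error.

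**The case against.** Several objections have force.

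- **Spread will be visible.** Item 8 already plans strata by drug and indication and a comparison of distributions, and section 9.7.1 makes median and IQR default summaries. This stands as far as it goes. But no criterion is attached to any of these, the verdict uses only the mean, and opposite deviations within one stratum still cancel. Comparing the distributions of observed and expected durations also does not show whether each patient's own pair agrees.
- **The rule does catch some wide spread.** At median one DDD and log-SD 0.7 the mean ratio is 1.28 and the rule fails. That is correct and limits the problem to moderate spread, spread offset by a higher median, or mixtures.
- **A per-patient band also picks up noise.** With one refill interval per father, everyone on exactly one DDD per day and an assumed refill-timing CV of 25%, only about 58% would fall in the band. Item 8 itself says that dose and compliance cannot be separated. This argues against a hard cut-off on the share, not against reporting it.

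A reader might infer three stronger things that the documents do not support. The first is that almost no father takes about one DDD per day. That needs a constructed mixture or a very wide spread, and no spread is given. The second is that the study would declare exposure misclassification to be of no concern. The protocol says no such thing: no exclusion, classification or model depends on the verdict, and item 8 has its own caveats. The third is that the primary hazard ratio is distorted. The primary contrast is binary and fitted irrespective of clusters (section 9.7.3.2.1), and accumulated DDDs are carried forward (footnote 10). For a father who refills regularly, an error in days per pack need not change his exposure group. No misclassification rate or shift in the hazard ratio has been computed.

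**Conclusion.** The point holds as a property of the stated rule. A mean outside 0.8 to 1.2 shows that one DDD per day fits badly, but a mean inside it does not show that one DDD per day fits individuals. With assumed log-SD of 0.3 to 0.5 around one DDD, the rule passes while 50% to 69% of fathers are outside the band; in a two-group mixture all could be.

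These figures rest on perfect compliance, on the ratio-of-sums definition and on spreads that are not in the protocol, so the true size is unknown. The consequence is an overstated validation claim. It matters most for supply reaching the edge of the exposure window, and for the k-means and cumulative-dose analyses. An effect on the primary comparison has not been shown.

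**What to change.** In item 8 of section 9.7.5:

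1. Compute each patient's ratio as a ratio of sums.
2. By drug and by epilepsy indication, report the median, the 10th and 90th percentiles and the share of per-patient ratios within 0.8 to 1.2, next to the mean.
3. Base the statement that the DDD approximates reality well on this per-patient distribution as well as the mean, and note that refill timing and imperfect compliance also widen it.
4. Describe a mean inside the band, taken alone, as average agreement only and not as validation for individuals.

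A fixed threshold for the share (two thirds, for example) and a rerun of exposure classification with each father's refill-based daily amount are optional. The threshold has no basis in the protocol, and refill amounts mix dose with compliance and timing.

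The cost is a wording change and one summary table from ratios that the analysis already needs. The validation may look less favourable.
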